# **Document History**

Document	Version Date
Original protocol	31 January 2023

# 1. PROTOCOL SUMMARY

# 1.1. Synopsis

**Protocol Title:** A Phase 1, Open-label, Fixed-sequence Study to Estimate the Effect of PF-07081532 Administration on the Single-Dose Pharmacokinetics of Dabigatran and Rosuvastatin in Overweight or Obese Adult Participants.

**Brief Title:** A Drug-Drug Interaction Study to Estimate the Effect of PF-07081532 on the Pharmacokinetics of Dabigatran and Rosuvastatin in Overweight or Obese Adult Participants.

# **Regulatory Agency Identification Number(s):**

**US IND Number:** 160296 (PF-07081532)

EudraCT Number: NA
ClinicalTrials.gov ID: NA
Pediatric Investigational Plan Number: NA

**Protocol Number:** C3991047

Phase:

**Rationale:** This is a Phase 1, open-label, fixed-sequence study to estimate the effect of PF-07081532 administration on the single-dose PK of dabigatran (total) and rosuvastatin in otherwise healthy overweight or obese adult participants. The intent of this study is to generate PK, safety, and tolerability data for further clinical development.

# **Objectives and Endpoints:**

Objectives	Endpoints				
Primary:	Primary:				
To estimate the effect of PF-07081532     administration on the single-dose PK of total dabigatran in otherwise healthy overweight or obese participants.	Dabigatran (total) PK parameters: AUC inf (if data permit* otherwise AUC last ) in Periods 1, 4, and 7.				
To estimate the effect of MD PF-07081532 on the single-dose PK of rosuvastatin in otherwise healthy overweight or obese participants.	Rosuvastatin PK parameters: AUC inf (if data permit* otherwise AUC last ) in Periods 2, 5, and 8.				
Secondary:	Secondary:				
To evaluate the safety and tolerability of PF-07081532 administered separately and in combination with DE in otherwise healthy overweight or obese participants.	
 
Assessment of TEAEs, clinical laboratory abnormalities, vital signs, body weight, and ECG parameters.
 
Assessment of mental health as determined by C-SSRS and PHQ-9.
 
				
To evaluate the safety and tolerability of PF-07081532 administered separately and in combination with rosuvastatin in otherwise healthy overweight or obese participants	
 
Assessment of TEAEs, clinical laboratory abnormalities, vital signs, body weight, and ECG parameters.
 
Assessment of mental health as determined by C-SSRS and PHQ-9.
 
				
To evaluate the effects of PF-07081532 on additional PK parameters for total dabigatran.	• Additional plasma PK parameters for total dabigatran: C max and T max ; and CL/F, Vz/F, t 1/2 as data permit, in Periods 1, 4, and 7.				
To evaluate the effects of PF-07081532 on additional PK parameters for rosuvastatin.	• Additional plasma PK parameters for rosuvastatin: C max and T max ; and CL/F, Vz/F, t 1/2 as data permit, in Periods 2, 5, and 8.				
To evaluate the MD pharmacokinetics of PF-07081532 in healthy overweight or obese participants.	PF-07081532 plasma pharmacokinetic parameters:     AUC 24 , C max , T max .				

\* Should it be deemed that too few  $AUC_{inf}$  estimates (eg, less than 16 for a single treatment) are obtained from the evaluable participants,  $AUC_{last}$  may be selected as the primary endpoint for CSR reporting. This will be considered for the dabigatran and rosuvastatin objectives separately.

# **Overall Design:**

This is a Phase 1, open-label, 8-period, fixed-sequence study to evaluate the effect of PF-07081532 administration on the single-dose PK of dabigatran (total) and rosuvastatin in otherwise healthy, overweight or obese, adult female or male participants. The 8 periods will be conducted sequentially without any washout days between periods.

# **Number of Participants:**

Approximately 24 participants will be enrolled in the study.

Note: "Enrolled" means a participant's, or their legally authorized representative's, agreement to participate in a clinical study following completion of the informed consent process and assignment to study intervention. A participant will be considered enrolled if the informed consent is not withdrawn prior to participating in any study activity. Potential participants who are screened for the purpose of determining eligibility for the study, but do not participate in the study, are not considered enrolled, unless otherwise specified by the protocol.

# **Study Population:**

Key inclusion and exclusion criteria are listed below:

# **Inclusion Criteria**

- 1. Participants aged 18 years or older (or the minimum age of consent in accordance with local regulations) at Screening.
  - Women can be of child-bearing potential, but cannot be pregnant, breastfeeding,
    or planning to become pregnant while participating in the study and may not be
    taking either oral contraceptives or non-oral hormonal contraceptives (with the
    exception of implantable progestogen only hormone contraception or intrauterine
    hormone releasing system), and must avoid vaccination with live attenuated
    vaccines.

Refer to Appendix 4 for reproductive criteria for male (Section 10.4.1) and female (Section 10.4.2) participants.

2. Male and female participants who are overtly healthy as determined by medical evaluation including detailed medical history, physical examination (including blood pressure and pulse rate measurement), standard 12-lead ECG, and clinical laboratory tests.

# **Other Inclusion Criteria:**

- 3. BMI:  $\geq 25 \text{ kg/m}^2$  at Screening.
- 4. Stable body weight, defined as <5 kg change (per participant report) for 90 days before Screening.

# **Exclusion Criteria**

Participants with any of the following characteristics/conditions will be excluded:

# **Medical Conditions**

- 1. Evidence or history of clinically significant hematological, renal, endocrine, pulmonary, gastrointestinal, cardiovascular, hepatic, psychiatric, neurological, or allergic disease (including drug allergies, but excluding untreated, asymptomatic, seasonal allergies at the time of dosing).
  - Any condition possibly affecting drug absorption (eg, prior bariatric surgery, gastrectomy, cholecystectomy or any area of intestinal resection, active inflammatory bowel disease or pancreatic insufficiency).
  - Other medical or psychiatric condition including recent or active suicidal ideation/behavior or laboratory abnormality that may increase the risk of study participation or, in the investigator's judgment, make the participant inappropriate for the study.
  - Known intolerance or hypersensitivity to a GLP-1R agonist(s), rosuvastatin, or DE.
- 2. Diagnosis of type 1 or type 2 diabetes mellitus or secondary forms of diabetes at screening. **Note:** women with prior diagnoses of gestational diabetes *during* pregnancy only are eligible if they meet the other eligibility criteria.
- 3. History of myocardial infarction, unstable angina, arterial revascularization, mechanical prosthetic heart valve, stroke, New York Association Functional Class II-IV heart failure, or transient ischemic attack within 6 months of Screening.
- 4. Any malignancy not considered cured (except basal cell carcinoma and squamous cell carcinoma of the skin); a study participant is considered cured if there has been no evidence of cancer recurrence in the previous 5 years (from Screening). Anyone with any history of pancreatic cancer will be excluded, even if it was resected and they were considered 'cured'.
- 5. Personal or family history of MTC or MEN2, or study participants with suspected MTC per the investigator's judgment.
- 6. Acute pancreatitis, a history of repeated episodes of acute pancreatitis, or history of chronic pancreatitis.
- 7. Symptomatic gallbladder disease.
- 8. Medical history or characteristics suggestive of genetic or syndromic obesity or obesity induced by other endocrinological disorders (eg, Cushing Syndrome).

- 9. History of major depressive disorder or history of other severe psychiatric disorders (eg, schizophrenia or bipolar disorder) within the last 2 years from screening.
- 10. Any lifetime history of a suicide attempt.
- 11. Known medical history of active liver disease (other than non-alcoholic hepatic steatosis), including chronic active hepatitis B or C, primary biliary cirrhosis, alcoholic liver disease, primary sclerosing cholangitis, autoimmune hepatitis, overlap syndrome, or prior known drug-induced liver injury.
- 12. History of HIV infection.
- 13. Recent history of bleeding, or risks of bleeding, including prior personal or familial history of abnormal bleeding, hereditary or acquired coagulation or platelet disorder, or abnormal coagulation test (INR >1.3) result at Screening.

# **Prior/Concomitant Therapy**

14. Use of any medications that are BCRP, OATP, P-gp and/or CYP3A4/5 inhibitors or inducers within 14 days or 5 half-lives (whichever is longer) prior to the first dose of study intervention (Refer to Section 6.9 for additional details).

# Diagnostic Assessments (at Screening unless otherwise indicated)

- 15. Screening supine BP ≥140 mm Hg (systolic) or ≥90 mm Hg (diastolic), following at least 5 minutes of supine rest. BP should be measured in triplicate and the average of the 3 BP values should be used to determine the participant's eligibility. Note: At Screening, the participant's arm circumference should be measured (eg, using a flexible anthropometric tape) at the midpoint of the length of the upper arm, and the appropriate cuff selected and used throughout the study.
- 16. Screening 12-lead ECG that demonstrates clinically relevant abnormalities that may affect participant safety or interpretation of study results (eg, QTcF interval >450 msec, complete LBBB, signs of an acute or indeterminate age myocardial infarction, ST-T interval changes suggestive of myocardial ischemia, second- or third-degree AV block, or serious bradyarrhythmias or tachyarrhythmias).
  - a. If QTcF exceeds 450 msec, or QRS exceeds 120 msec, the ECG should be repeated 2 more times and the average of the 3 QTcF or QRS values should be used to determine the participant's eligibility. Computer interpreted ECGs should be overread by a physician experienced in reading ECGs before excluding participants.
- 17. Participants with ANY of the following abnormalities in clinical laboratory tests at Screening, as assessed by the study specific laboratory and confirmed by a single repeat test, if deemed necessary:

- HbA1c  $\geq$ 6.5%.
- AST or ALT level  $\geq 1.25 \times$  ULN.
- Total bilirubin level ≥1.5× ULN; participants with a history of Gilbert's syndrome may have direct bilirubin measured and would be eligible for this study provided the direct bilirubin level is ≤ ULN.
- TSH >1.5x ULN or < LLN.
- INR >1.3.
- Serum calcitonin > ULN.
- Amylase or lipase > ULN.
- Fasting blood glucose ≥126 mg/dL.
- Fasting C-peptide not WNL.
- eGFR <75 mL/min/1.73 m2 as calculated by the CKD-EPI equation.
- Positive testing for HIV, HBsAg, HBcAb, or HCVAb. Study participants positive
  for HCVAb are to be excluded unless known to have been treated with a known
  curative therapy and negative for HCV RNA. Anyone who has a history of HBV
  that is treated/cleared is excluded. Hepatitis B vaccination is allowed.
- A positive SARS-CoV-2 test.

# **Study Arms and Duration:**

The total duration of participation from the Screening Visit to the F/U outpatient telephone contact will be approximately 115 days or 16.5 weeks, approximately 8 weeks of which will be conducted on an inpatient basis.

The 54-day inpatient portion of the study will be conducted as follows:

Period 1: 3 days, includes CRU admission on Day -1 (DE 150 mg single dose);

Period 2: 4 days (rosuvastatin 10 mg single dose);

Period 3: 8 days (PF-07081532 titrated to 40 mg QD);

Period 4: 5 days (DE 150 mg single dose + PF-07081532 80 mg QD);

Period 5: 4 days (rosuvastatin 10 mg single dose + PF-07081532 80 mg QD);

Period 6: 20 days (PF-07081532 titrated to 260 mg QD);

Period 7: 5 days (DE 150 mg single dose + PF-07081532 260 mg QD);

Period 8: 5 days, includes discharge day from CRU (rosuvastatin 10 mg single dose + PF-07081532 260 mg QD).

The onsite F/U visit/telephone F/U contact will occur 7-10 days from the last dose of study intervention (Period 8, Day 4) and an outpatient telephone F/U contact will occur 28-35 days from the last dose of study intervention (Period 8, Day 4).

Study Interventions						
Intervention Name	PF-07081532	Rosuvastatin	DE			
Arm Name (group of participants receiving a specific treatment or no treatment)	All participants	All participants	All participants			
Unit Dose Strength	20 mg, 60 mg, 100 mg	10 mg	150 mg			
Route of Administration	Oral	Oral	Oral			
Use	Perpetrator	Substrate	Substrate			
IMP or NIMP/AxMP	IMP	NIMP/AxMP	NIMP/AxMP			

				Study A	rms			
Arm Title	Period 1: single-dose DE	Period 2: single-dose rosuvastatin	Period 3: PF-07081532 titration	Period 4: single-dose DE + PF-07081532	Period 5: single-dose rosuvastatin + PF-07081532	Period 6: PF-07081532 titration	Period 7: single-dose DE + PF-07081532	Period 8: single-dose rosuvastatin + PF-07081532
Arm Type	Baseline	Baseline	IMP titration only	Experimental (DDI)	Experimental (DDI)	IMP titration only	Experimental (DDI)	Experimental (DDI)
Arm Description	Participants will receive a single 150 mg dose of DE.	Participants will receive a single 10 mg dose of rosuvastatin.	Participants will receive PF-07081532 titrated from 20 mg QD to 40 mg QD over a total of 8 days.	Participants will receive a single 150 mg dose of DE with 80 mg PF-07081532 QD.	Participants will receive a single 10 mg dose of rosuvastatin on a background of 80 mg PF-07081532 QD.	Participants will receive PF-07081532 titrated from 120 mg QD to 260 mg QD over a total of 20 days.	Participants will receive a single 150 mg dose of DE with 260 mg QD PF-07081532.	Participants will receive a single 10 mg dose of rosuvastatin on a background of 260 mg QD PF-07081532.

Based on emerging data from other clinical studies that may become available during the conduct of this study, the titration rate, incremental increases in dose, and/or the PF-07081532 doses at which rosuvastatin and/or dabigatran PK interactions are evaluated may be adjusted. If participants are not able to tolerate titration to higher doses of PF-07081532 (eg,  $\geq$ 180 mg QD), titration to the next dose level may be delayed temporarily or titration to a maximum tolerated dose may be permitted, with sponsor approval only.

# **Statistical Methods:**

The PK data for PF-07081532, rosuvastatin, and dabigatran will be analyzed and reported separately.

Approximately 16 evaluable participants will complete the study.

Natural loge transformed AUCinf (as data permit), AUClast and Cmax of rosuvastatin administered without PF-07081532 or coadministered with PF-07081532 will be analyzed using a mixed effect model with treatment as a fixed effect and participant as a random effect. Estimates of the adjusted mean differences (Test/Reference) and corresponding 90% CIs will be obtained from the models. The adjusted mean differences and 90% CIs for the differences will be exponentiated to provide estimates of the ratio of adjusted geometric means (Test/Reference) and 90% CIs for the ratios. The 2 test treatments will be 'rosuvastatin and PF-07081532 80 mg QD' (Period 5) and 'rosuvastatin and PF-07081532 260 mg QD' (Period 8), which will be reported separately in comparison to the reference treatment of 'rosuvastatin without PF-07081532' (Period 2).

Natural loge transformed AUC $_{inf}$  (as data permit), AUC $_{last}$  and C $_{max}$  of dabigatran administered alone or coadministered with PF-07081532 will be analyzed and reported separately using the same mixed effect model as described above for rosuvastatin. For dabigatran, the 2 test treatments will be 'dabigatran and PF-07081532 80 mg QD' (Period 4) and 'dabigatran and PF-07081532 260 mg QD' (Period 7), which will be reported separately in comparison to the reference treatment of 'dabigatran alone' (Period 1).

[figure not shown]
# **Ethical Considerations:**

PF-07081532 is not expected to provide any long-term clinical benefit to the healthy obese adult female and male participants in this study. This study is designed primarily to generate safety, tolerability, and PK data for further clinical development.

Based on experience with PF-07081532 and other marketed GLP-1R agonists, the potential risks for PF-07081532 include thyroid C-cell tumors, pancreatitis, hypoglycemia, renal function impairment, gastrointestinal adverse reactions, diabetic retinopathy complications, suicidal ideation and behavior, changes in heart rate and blood pressure, weight loss, and/or acute gallbladder disease.

Participants will be expected to commit time and may experience some discomfort while undergoing study assessments. In addition, participants of childbearing potential must agree to use appropriate contraception methods and avoid vaccination with live attenuated vaccines.

# 1.2. Schema

# 1.3. Schedule of Activities

The SoA table provides an overview of the protocol visits and procedures. Refer to the STUDY ASSESSMENTS AND PROCEDURES section of the protocol for detailed information on each procedure and assessment required for compliance with the protocol.

The investigator may schedule visits (unplanned visits) in addition to those listed in the SoA table, in order to conduct evaluations or assessments required to protect the well-being of the participant.

Table 1. Overall Schedule of Activities Screening to Period 5

Visit Identifier Abbreviations used in this table may be found in Appendix 9	Screening		Period 1 Period 2 Period 3 (PF-07081532 only)		Per (PF-07082	Period 5 (PF-07081532 + ROSU)				
Day in Study Period a	-28 to -2	-1	1-2	1-4	1	2-7	8	1-4	5	1-4
Days in Study b	-28 to -2	-1	1-2	3-6	7	8-13	14	15-18	19	20-23
Informed consent and demography	X									
Outpatient visit (after ≥10 h fast)	X									
Medical history	X									
Eligibility criteria	X	X								
Physical exam c (height at Screening only)	X									
Review contraception use - WOCBP Only (Section 5.3.1)	X	X								
Review drug, alcohol/tobacco use	X	X								
COVID-19 screening d		X								
C-SSRS and PHQ-9	X	X					X			
Review prior or concomitant treatments	X	X	$\rightarrow$	$\rightarrow$	$\rightarrow$	$\rightarrow$	$\rightarrow$	$\rightarrow$		$\rightarrow$
AE monitoring	X	X	$\rightarrow$	$\rightarrow$	$\rightarrow$	$\rightarrow$	$\rightarrow$	$\rightarrow$	$\rightarrow$	$\rightarrow$
Inpatient stay at CRU		X	$\rightarrow$	$\rightarrow$	$\rightarrow$	$\rightarrow$	$\rightarrow$	$\rightarrow$	$\rightarrow$	$\rightarrow$
Body weight	X	•	X 		X l		X l			$X^{l}$
Supine 12-lead ECG	X		XI				X l			
Single, supine vital signs assessment e	X		X l		X l		X l			X 

Table 1.	Overall Schedule of Activities Screening to Period 5
----------	--

Visit Identifier Abbreviations used in this table may be found in Appendix 9	Screening		riod 1 Conly)	Period 2 (ROSU only)	(PF-	Period 3 07081532	only)		iod 4 1532 + DE)	Period 5 (PF-07081532 + ROSU)
Day in Study Period a	-28 to -2	-1	1-2	1-4	1	2-7	8	1-4	5	1-4
Days in Study b	-28 to -2	-1	1-2	3-6	7	8-13	14	15-18	19	20-23
Rosuvastatin administration				Table 4						Table 4
DE administration			Table 3					Table 3		
PF-07081532 administration f					X	X	X	1	Table 5	Table 4
PF-07081532 PK										
Rosuvastatin PK				Table 4	Xg					1
Dabigatran PK			Table 3	1 1				Table 3		
CCI										
Blood Sampling for:h										
- Chemistry	X	X					X			
- Calcitonin, amylase, lipase	X	X					X			
- Free T4, TSH, lipid panel, total bile acids	X	X	_							
- Hematology/ HbA1c	X	X					X			
- FSH i , HIV, HBsAg, HCVAb, HCV RNA, C-peptide	X									
- PT/INR	X									
- Serum pregnancy test i	X	X								
CCI										
Urine Sampling for:										
- Urine drug test k	X	X								
- Urinalysis (and microscopy, as appropriate)	X									

# Table 1. Overall Schedule of Activities Screening to Period 5

Visit Identifier Abbreviations used in this table may be found in	Screening	Peri (DE		Period 2 (ROSU only)		Period 3 7081532	only)		iod 4 1532 + DE)	Period 5 (PF-07081532
Appendix 9		,	• •		,		• *	`	•	+ ROSU)
Day in Study Period a	-28 to -2	-l	1-2	1-4	1	2-7	8	1-4	5	1-4
Days in Study b	-28 to -2	-1	1-2	3-6	7	8-13	14	15-18	19	20-23

- Day relative to start of dosing Day 1 of that Period.
- Day relative to first dose of investigational product (DE) on Day 1 of Period 1.
- Complete physical exam at Screening, otherwise, brief exam if findings during previous exam or new/open AEs, if appropriate, at investigator discretion.
- d. Participants will be screened for COVID-19 according to local procedures prior to being admitted to the clinic for confinement in Period 1. Subsequent testing will also be done according to local procedure if participants develop COVID-19 like symptoms. See also Section 8.3.5 (COVID-19 Specific Assessments). If a participant tests positive for SARS-CoV-2 infection, they will be discharged from the study.
- e. Includes BP and PR predose.
- Dosing to occur QD with breakfast as specified in Section 6.1.1.
- g. The rosuvastatin PK sample is to be collected predose (0 hr) on Day 1 of Period 3.
- Collection following fasting duration specified in Section 5.3.2.
- FSH for female participants to confirm PM status only. Serum β-hCG for all WOCBP; test result should confirm no pregnancy prior to dosing.

### CC

- k. Participants may undergo random urine drug testing at the discretion of the investigator.
- Assessments to be done on Day 1 of Periods 1, 3, and 5 and prior to IP administration on all days indicated.

Table 2. Overall Schedule of Activities Period 6 to ET

Visit Identifier Abbreviations used in this table may be found in Appendix 9			riod 6 81532 only	7)	Perio (PF-070) DI	81532 +	(PF-07	riod 8 7081532 + OSU)	F/U Visit q	F/U Contact Telephone	ET
Day in Study Period a	1-5	6-10	11-15	16-20	1-4	5	1-4	5	7-10	28-35	-
Days in Study b	24-28	29-33	34-38	39-43	44-47	48	49-52	53 f	59-62	80-87	-
Outpatient visit (after ≥10 hr fast)									X		
Physical exam											Χ°
Review contraception use - WOCBP Only (Section 5.3.1)									X	X	
Review drug, alcohol/tobacco use									X		
COVID-19 screening d											
C-SSRS and PHQ-9°	X			X				X	X		X
Review prior or concomitant treatments	$\rightarrow$	$\rightarrow$	$\rightarrow$	$\rightarrow$	_	<del>}</del>	$\rightarrow$	X	X	X	
AE monitoring	→	$\rightarrow$	$\rightarrow$	$\rightarrow$	_	>	$\rightarrow$	X	X	X	
Inpatient stay at CRU	→	$\rightarrow$	$\rightarrow$	$\rightarrow$	_	<del>}</del>	+	Xi			
Body weight g	X		X	X				Xi	X		X
Supine 12-lead ECG		Xh						$X^{i}$			X
Single, supine vital signs assessment	X		X	X				Xi	X		X
Blood Sampling for: k											
- Chemistry	X 			X 				X i	X		X
- Calcitonin, amylase, lipase				$X^1$				Xi			X
- Free T4, TSH, lipid panel, total bile acids								Xi	1		X
- Hematology/HbA1c				X 				Xi	X		X
- Serum pregnancy test m								Xi			
Rosuvastatin administration							Table 4				
DE administration					Table 3						
PF-07081532 administration n	→	→	→	→	1	Table 5	Table 4				
PF-07081532 PK						1					X
Rosuvastatin PK	Χ°						1	Table 4			
Dabigatran PK					Table 3						
CCI											
Urine Sampling for:											
- Urine drug test p											
- Urinalysis (and microscopy, as appropriate)											X

a. Day relative to start of dosing Day 1 of that Period.

b. Day relative to first dose of investigational product (DE) on Day 1 of Period 1.

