# Table 2. Overall Schedule of Activities Period 6 to ET

Visit Identifier Abbreviations used in this table may be found in Appendix 9			riod 6 81532 only	·)	Perio (PF-0708 DF	81532 +	(PF-07	riod 8 7081532 + OSU)	F/U Visit q	F/U Contact Telephone	ET
Day in Study Period a	1-5	6-10	11-15	16-20	1-4	5	1-4	5	7-10	28-35	-
Days in Study b	24-28	29-33	34-38	39-43	44-47	48	49-52	53 f	59-62	80-87	-

- c. Brief exam if findings during previous exam or new/open AEs, if appropriate, at investigator discretion.
- d. Participants will be screened for COVID-19 according to local practice prior to being admitted to the clinic for confinement in Period 1. A subsequent test will be done according to local procedure if participants develop COVID-19 like symptoms. See also Section 8.3.5 (COVID-19 Specific Assessments). If participants test positive for SARS-CoV-2 infection, they will be discharged from the study.
- e. C-SSRS and PHQ-9 will be administered in Period 6 on Days 5 and 19, and in Period 8 on Day 5 (discharge from CRU).
- f. Discharge from CRU.
- g. Body weight to be obtained on Days 5, 12 and 19 in Period 6.
- h. ECG to be obtained on Day 10 of Period 6.
- i. Assessments to be obtained on Day 5 of Period 8 prior to D/C from the CRU.
- j. Includes BP and PR predose; to be obtained on Days 5, 12 and 19 in Period 6.
- k. Collection following fasting duration specified in Section 5.3.2.
- 1. Chemistry to be obtained on Days 1 and 20 in Period 6; calcitonin, amylase, lipase and hematology to be obtained on Day 20 in Period 6.
- m. Serum β-hCG for all WOCBP
- n. Dosing to occur QD with breakfast. Note that there is no PF-07081532 administration on Study Day 53 or anytime thereafter.
- o. The rosuvastatin PK sample is to be collected predose (0 hr) on Day 1 of Period 6.
- p. Participants may undergo random urine drug testing at the discretion of the investigator.
- q. The follow-up visit 7-10 days after the last dose of study intervention (Period 8, Day 4) can be on-site or via telephone call. Whether the follow-up visit is on-site or via telephone call is at the discretion of the Investigator. Regardless of location (ie, on site or telephone call), contraception use, drug, alcohol/tobacco use, concomitant medications and AEs must be reviewed/assessed as appropriate.

Table 3. Schedule of Activities – Period 1 (DE ONLY), Period 4 (DE + PF-07081532 80 mg QD) and Period 7 (DE + PF-07081532 260 mg QD)

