# 2.2.4.1. Clinical Pharmacokinetics

The clinical PK of PF-07081532 in adult participants have been evaluated to date in 2 completed studies (C3991001 and C3991002). The results of these completed studies are summarized in the PF-07081532 IB.

In Study C3991001 following administration of single oral doses of PF-07081532 under fasted conditions to healthy participants, PF-07081532 was absorbed relatively rapidly with a median  $T_{max}$  of 1.00 to 4.02 hours (individual  $T_{max}$  values ranged between 0.5 and 6 hours). Based on the individual plasma concentration-time profiles, the absorption phase exhibited multiple peaks, especially at the higher dose levels. Mean  $t_{1/2}$  ranged from 18.03 to 20.90 hours across all doses. Plasma  $C_{max}$  increased less than proportionally across the entire investigated dose range (from 10 mg to 200 mg), while plasma AUCinf increased less than proportionally from 10 mg to 30 mg and approximately proportionally from 30 mg to 200 mg. Inter-participant variability for PF-07081532 exposure was low to moderate and ranged from 9% to 36% CV for  $C_{max}$  and 15% to 44% CV for AUCinf across all doses. Overall, the results indicate that PF-07081532 may be administered without regard to food.

In Study C3991002 following administration of PF-07081532, Cmax was observed at 1 to 2 hours on Day 1, and 2 to 8 hours following the last dose on Day 28 or 42. Across all dose groups, the mean t½ ranged from 20.70 to 26.50 hours. PF-07081532 exposure generally increased in an approximately dose-proportional manner across the dose range studied, and accumulation of less than 2.1-fold was observed. Urinary recovery of unchanged PF-07081532 was low, with less than 0.2% of the dose recovered in the 24-hour dosing interval following last dose administration. Inter-participant variability for PF-07081532 exposure ranged from 17% to 51% CV for Cmax and 15% to 62% CV for AUCtau across all doses. No substantial differences in PF-07081532 exposure (Cmax and AUCtau) were observed between participants with T2DM and obesity either after single dose (Day 1, 10 mg) or multiple dose (Day 28, 120 mg and Day 42, 180 mg) administration.

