Suicidal ideation and behavior	The potential risk is based on the product labeling for the injectable GLP-1R agonists liraglutide and semaglutide for obesity based on long-term studies.  Suicidal ideation has not been observed in the PF-07081532 clinical studies to date.	Suicidal ideation and behavior, along with symptoms of depression, will be monitored at specified intervals during the study using the C-SSRS and PHQ-9 questionnaires, with referral to a MHP for further evaluation if needed.
Changes in heart rate	Potential risk is based on the product labeling for the injectable GLP-1R agonists, liraglutide and semaglutide, for T2DM and obesity.	HR is monitored during the clinical study.
	Modest increases in HR have been noted in the early clinical studies with PF-07081532, with most values remaining within the normal range.	

Declines in body weight  Decreased appetite and body weight loss have been reported for marketed GLP-1R agonists, and declines in body weight have been noted at higher doses of PF-07081532.  Acute gallbladder disease  Potential risk is based on the product labeling for the injectable GLP-1R	Weight is collected at multiple time points and will be monitored throughout the trial.  Participants with symptomatic gallbladder disease are excluded from this clinical study.
	gallbladder disease are excluded
agonists, semaglutide and liraglutide, for T2DM and obesity.  Acute gallbladder disease has not been observed in the PF-07081532 clinical trial program to date.	Participants are monitored for AEs and laboratory tests that may suggest development of acute gallbladder disease.
Study Intervention: Rosuvastatin	

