Period 8, Days 1-5*	49-53*	PF-07081532 260 mg QD + SD Rosuvastatin 10 mg

\*No drug administration in Period 8, Day 5 (Study Day 53); participants discharged from the CRU.

Modification of PF-07081532 dosing may be permitted **upon sponsor approval only** (see Section 6.6).

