### 9.3.4.1. Electrocardiogram Analyses

Changes from baseline for the ECG parameters QT interval, heart rate, QTcF interval, PR interval, and QRS complex will be summarized by treatment and time.

The number (%) of participants with maximum postdose QTcF values and maximum increases from baseline in the following categories will be tabulated by treatment:

 Table 12.
 Safety QTcF Assessment

Degree of Prolongation	Mild (msec)	Moderate (msec)	Severe (msec)
Absolute value	>450-480	>480-500	>500
Increase from baseline		30-60	>60

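### No scheduled ECG, pulse or blood pressure reading on PF-07081532 is timed to its stated peak; the untimed Period 6 Day 10 ECG could be fixed there at little cost

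*Protocol*

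**What the plan says.** **Periods 1 to 5 (Protocol Section 1.3, Table 1).** The timing footnote for ECG and vital signs reads "Assessments to be done on Day 1 of Periods 1, 3, and 5 and prior to IP administration on all days indicated". The vital-signs row carries a further footnote: "Includes BP and PR predose".

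**Period 6 (Table 2).** Footnote j, for vital signs, reads "Includes BP and PR predose; to be obtained on Days 5, 12 and 19 in Period 6". Footnote h places one ECG on Day 10 and gives no time relative to dose.

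**Period 8 (Table 2).** Footnote i reads "Assessments to be obtained on Day 5 of Period 8 prior to D/C from the CRU". Table 2 footnote n and Table 8 state that no drug is given that day, so the last dose was on Day 4.

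**Hour-by-hour tables.** Tables 3 to 5 are the only ones set out in hours relative to dosing. They list dosing and blood sampling, with no ECG or vital signs.

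**Peak (Protocol Section 2.2.4.1).** In C3991002, Cmax came at 1 to 2 h on Day 1 "and 2 to 8 hours following the last dose on Day 28 or 42". In C3991003, multiple-dose Tmax was 2 to 5 h.

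**Use of the readings.** Protocol Section 9.3.4.1 tabulates, by treatment, "participants with maximum postdose QTcF values and maximum increases from baseline". SAP 6.2.1.3 and 6.2.1.4 summarise maximum vital-sign and ECG values over planned and unplanned time points after dosing. Protocol Section 2.3.1 names heart-rate change as a risk, notes modest increases already seen, and gives as mitigation "HR is monitored during the clinical study".

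**The concern.** ECG and vital signs are named secondary safety endpoints, and heart rate is a risk with a signal already observed. A table of maximum QTcF or pulse by treatment invites the reader to take the maximum as covering the dosing interval. If every planned reading with a stated time sits at the low end of that interval, a rise that follows concentration would be seen at reduced size or missed, and nothing in the table title would say so.

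This matters most at the upper doses. Protocol Section 2.2.4 describes multiple doses up to 180 mg QD in completed studies. This study was planned to 260 mg QD, and SAP Section 2.1 reports a cap at 240 mg QD.

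**Working it through.** **Step 1. Tally of scheduled on-drug readings**, first PF-07081532 dose to discharge (Tables 1, 2 and 8).

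| Reading | ECG | Pulse/BP | Time relative to PF-07081532 dose |
|---|---|---|---|
| Period 3 Day 8 | yes | yes | predose |
| Period 5 Day 1 | no | yes | predose |
| Period 6 Days 5, 12, 19 | no | yes (3 sets) | predose |
| Period 6 Day 10 | yes | no | not stated |
| Period 8 Day 5 | yes | yes | about 24 h after last dose |

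The Period 1 Day 1 readings, and the Period 3 Day 1 vital signs, precede any PF-07081532. The follow-up vital signs come 7-10 days after the last dose. ET readings have no stated time.

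- ECGs with a stated time: 2, of which 0 fall at 2-8 h.
- Pulse/BP sets with a stated time: 1 + 1 + 3 + 1 = 6, of which 0 fall at 2-8 h.
- ECGs with no stated time: 1 (Period 6 Day 10), plus any at ET.

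Periods 3, 6 and 8 each hold one scheduled ECG. Unless unplanned or ET readings are added, the maximum for each of those treatments is a single value.

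**Step 2. How far below peak is a 24 h reading?** The plan gives no figure for this. Inputs from Protocol Section 2.2.4.1: multiple-dose mean half-life 20.70-26.50 h and Tmax 2-8 h (C3991002); half-life 24.37-26.04 h and Tmax 2-5 h (C3991003). With mono-exponential decline after the peak, which is an assumption here, the 24 h level as a fraction of Cmax is 2^(−(24 − Tmax)/t½).

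| t½ (h) | Tmax 2 h | Tmax 5 h | Tmax 8 h |
|---|---|---|---|
| 20.70 | 0.479 | 0.529 | 0.585 |
| 24.37 | 0.535 | 0.583 | 0.634 |
| 26.04 | 0.557 | 0.603 | 0.653 |
| 26.50 | 0.562 | 0.608 | 0.658 |

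The full range is 48% to 66%. With the C3991003 figures alone it is 54% (24.37 h, 2 h) to 60% (26.04 h, 5 h). A predose reading under once-daily dosing is also about 24 h after the previous dose, so the same fractions apply relative to that dose's peak.

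**Step 3. In dose terms.** Section 2.2.4.1 describes exposure as approximately dose-proportional. After 240 mg QD, the Period 8 Day 5 level matches the peak at 0.479 × 240 = 115 mg to 0.658 × 240 = 158 mg QD. After 260 mg QD, it matches 0.479 × 260 = 125 mg to 0.658 × 260 = 171 mg QD. Both ranges lie below 180 mg QD.

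**Step 4. Where the untimed ECG falls.** Period 6 Day 10 is within Days 9-12, which Table 8 gives as 200 mg QD. That is above the 180 mg QD maximum in completed studies and below this study's top dose.

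**The case against.** The strongest reply is that this is a transporter interaction study with PK primary endpoints and no hypothesis test, and that it nowhere claims to characterise QTc or pulse at peak. Baseline is the last pre-dose value in Period 1 (SAP 3.2.1), so any later reading is after dosing in the ordinary sense. The SAP knows some readings precede that day's dose: it assigns pre-dose Day 1 values to the previous period's treatment. Protocol Sections 8.3 and 8.3.2.1 allow unscheduled measurements and changed collection times, and the SAP counts unplanned readings. Prior heart-rate increases were modest. All of this stands, and it limits the importance of the point. It does not supply a planned reading at peak.

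A reader might infer more than the documents support:

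- **That all on-drug ECGs, and so the repeat-ECG rule in Protocol Section 8.3.3, see only near-trough values.** The Period 6 Day 10 and ET ECGs are untimed and could fall at any hour. The rule's second limb, an absolute QT threshold, applies to any scheduled ECG.
- **That both documents title their tables as postdose maxima.** Only Protocol Section 9.3.4.1 does so. The SAP refers to maximum absolute values and changes from baseline.
- **That the tables are biased toward no effect.** That needs a concentration-response relationship for QTcF or pulse, and none is given.
- **That the predose pulse and BP readings should all move to the peak window.** This would lose the like-for-like comparison with a fasted, predose baseline, with no placebo or time-matched control to separate drug from meal and time of day. On Period 6 Day 5, the first 160 mg day, it would also replace a reading that follows four days at 120 mg with one after the first 160 mg dose.

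**Conclusion.** The point holds in a limited form. No scheduled ECG, pulse or BP reading is timed to the stated multiple-dose peak. The pulse/BP readings during confinement and the two timed ECGs are predose or about 24 h after the last dose, at roughly half to two-thirds of peak concentration (48-66%). A peak reading may occur through the Day 10 ECG, an ET visit or an unplanned measurement, but the schedule does not provide for one.

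The tally rests on the schedule footnotes alone. The percentages rest on mono-exponential decline and on half-life and Tmax from earlier studies. SAP Section 2.1 says the study was shortened by 6 days and that its presented design is not current for dose and execution day, so the late-study timings as carried out cannot be confirmed. The consequence is incomplete secondary safety information and a table that can be over-read. The primary PK comparison is unaffected.

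**What to change.** 1. **Time the existing ECG.** In Table 2 footnote h, set the Period 6 Day 10 ECG at one fixed time within 2-8 h after dosing, for example just before the lunch that Protocol Section 5.3.2 places about 4 h after dosing. That hour lies inside both stated Tmax ranges. The ECG also yields heart rate (Section 8.3.3), so one reading covers both measures.
2. **Keep the predose pulse and BP readings** for comparability with baseline.
3. **Label the outputs.** In Protocol Section 9.3.4.1 and SAP 6.2.1.3 and 6.2.1.4, identify the predose and 24 h readings as near-trough, and do not present their maxima as covering peak exposure.
4. **If Period 6 is already complete**, report the Day 10 ECG by actual time since dose, where recorded, and state that peak exposure was not systematically assessed. SAP version 2 records that sufficient participants reached 240 mg QD, so this may be the only route left.

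The cost is one footnote and some table text. No procedure is added, participants are inpatient, and no reading with a fixed time is displaced. The Day 10 value will differ from the fasted, predose Period 1 baseline in meal state and time of day, which needs a note. It would describe the peak at 200 mg QD, so the top dose would still have no planned peak reading.
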